6.5.4 Wearable data

6.5.4.1 DynaPort

The analysis of the DynaPort data will be performed on on the DES population.

Summary statistics for the wearing time of DynaPort data will be presented by cohort and wearing period.

The following parameters (mean, minimum and maximum over wearing period) will be analyzed:

- Steps
- Physical Activity Level (PAL)
- Total Energy Expenditure (TEE)

- Active time (Sum of standing, shuffling, walking, stair walking and cycling time)
- Time spent in different activity states (sedentary / light / moderate / vigorous)

The DynaPort parameters mentioned above will be summarized by cohort/total and visit using descriptive statistics including arithmetic mean, SD, median, minimum and maximum.

Statistics will be presented for the original data and difference to baseline.

Graphical displays of individual data as well as mean values with standard deviations will be created for each parameter by cohort using planned sampling times.

The univariate LMM for the repeated values of the DynaPort parameters is

$$Y_{ij} = \mu + S_i + v_j + \beta base_i + E_{ij}$$

where μ is a constant common to all observations, S_i is the normally distributed random variable with mean zero and variance σ_d^2 corresponding to subject i , v_j is the fixed effect corresponding to visit j , and E_{ij} is a normally distributed random variable with mean zero and variance σ_e^2 , independent of S_i . The variable “base” is the baseline measurement included as covariate and β is the corresponding regression parameter.

Based on the described LMM, point estimates and 90% confidence intervals for the DynaPort parameters will be calculated.

Subgroup analyses will be performed for the defined categories (worsening / no worsening) of 6MWD, KCCQ and PRO.

7. Document history and changes in the planned statistical analysis

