### Justification of the design

The open study design is considered acceptable and justified, because the variables of the study are objectively measured results that are unlikely to be subject to investigator or study patient induced bias.

Male and female patients will be enrolled into this study. There are no reasons to date (i.e. safety reasons) to exclude women from these investigations.

The chosen study design is considered to be appropriate to establish a baseline for potential further objectives for the evaluation of efficacy of treatment responses in patients with heart failure, particularly HFpEF. The statistical analysis of this trial is performed in an exploratory manner.

This pilot study serves as a preparatory study designed to test the performance characteristics and capabilities of new measures, procedures, recruitment criteria, and operational strategies that are under consideration for use in a subsequent, larger, interventional study; cohort study is the appropriate study design for this pilot study. The aims and methods of this pilot study are aligned with the goals of potentially subsequent studies in BAYER's target indications. The study will contribute to the development and design of future studies by clarifying and sharpening the research hypotheses to be studied, assessing the clinical utility of emerging readouts, identifying relevant factors that could create barriers to subsequent study completion, evaluating the acceptability of methods and instruments to participants, measuring the time required for study participation, and providing concrete estimates of the expected rates of missing data and participant attrition.

In addition, the study aims to estimate baseline values and standard deviation of potential pharmacodynamic outcome measures related to the physical activity (e.g. movement intensity, daily steps) to give information for sample size calculations in subsequent trials. Furthermore, the study will improve the understanding of study questionnaires or data collection tools

However, results from these kinds of studies can be influenced by unpredictable confounding factors.

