## 6. Study population

### 6.1 Inclusion criteria - amended

1. Written informed consent signed before any study-specific procedure
2. Men or women aged 45 years and older
3. Established diagnosis of chronic heart failure NYHA class II-IV
4. Worsening heart failure requiring hospitalization for the initiation of intensification of heart failure therapy with **at least one** of the following
  - BNP  $\geq$  100 pg/mL or NT-proBNP  $\geq$  400 pg/mL (sinus rhythm) or BNP  $\geq$  300 pg/mL or NT-proBNP  $\geq$  1200 pg/mL (atrial fibrillation)
  - Radiographic evidence of pulmonary congestion (interstitial edema, pulmonary venous hypertension, vascular congestion, pleural effusion)
  - Catheterization documented elevated filling pressures at rest (left ventricular end-diastolic pressure  $\geq$ 15 mmHg or pulmonary capillary wedge pressure  $\geq$ 20 mmHg) or with exercise (pulmonary capillary wedge pressure  $\geq$ 25 mmHg)

OR

Ambulatory patients with a history of heart failure on individually optimized treatment with HF medications unless contraindicated or not tolerated, for at least 12 weeks and **at least one** of the following

- Hospitalization for heart failure within the past 12 months or
- BNP  $\geq$  100 pg/mL or NT-proBNP  $\geq$  400 pg/mL (sinus rhythm) or BNP  $\geq$  300 pg/mL or NT-proBNP  $\geq$  1200 pg/mL (atrial fibrillation)

---

 Inclusion criteria extended to ambulatory subjects with chronic heart failure as per Amendment 3 (Section 15.3)

5. For HFrEF only
  - EF  $\leq$  35% assessed by any imaging modality (e.g. echocardiography, cardiac magnetic resonance, cine levocardiography) within 12 months prior to study inclusion
6. For HFpEF only
  - EF  $\geq$  45% assessed by any imaging modality (e.g. echocardiography, cardiac magnetic resonance, cine levocardiography) within 12 months prior to study inclusion
7. Willingness to wear the DynaPort Move Monitor accelerometer belt and VitalPatch biosensor during the trial
8. Body size allows wearing of the accelerometer belt as confirmed by ability to comfortably fasten the test belt provided for the screening process

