##### **Modification 1: Extension of the study population**

*Description of modification to the study plan:*

In- and exclusion criteria were modified to allow participation of a wider range of patients with heart failure.

*Rationale for introducing the modification:*

Ambulatory, stable patients were added to the study population to also gain further insights into this group, in comparison to the hospitalized patients with worsening heart failure. The data generated is meant to be used as reference for future clinical development projects across various different heart failure subpopulations, to cover the complete clinical spectrum and various characteristics of the patient journey.

In addition, entry criteria were adjusted to match the situation of the subjects in scope. Specifically, the exclusion criterion for hemoglobin was changed from <10.0 g/dL to <8.0 g/dL. Low hemoglobin values are commonly observed due to dilution of the blood from excess fluid. Through application of standard diuretic therapy, it is expected that hemoglobin levels will quickly recover, and hemoglobin will not have an impact on exercise capacity.

*List of all CSP sections affected by this modification:* Sections 2, 5, 6.1, 6.2.

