- Explore the relationship between PA, 6-minute walking distance (6MWD), PRO, biomarkers, adverse events/clinical outcomes
- Investigate the accuracy of patients' self-reports (PRO, e.g. KCCQ) of time spent on PA in real life vs. objective assessment by the DynaPort Move Monitor and VitalPatch biosensor³

¹ Will not be addressed due to change from AVIVO to VitalPatch (ECG data only)

² Will not be addressed due to change in procedure schedule

³ Meaningful assessment not possible given the provided variables.

Given the data situation (not all parameters provided by the vendor) and the low number of subjects (recruiting stopped early due to recruiting issues), not all the original objectives mentioned above will be addressed.

3. Study Design

This is a non-randomized, multi-center, observatory prospective patient study. The study will be conducted in several centers in EU and non-EU.

[figure not shown]
Patients hospitalized due to heart failure as well as ambulatory patients with heart failure will be included in this study. Overall approx. 80 subjects have to complete at least all device monitoring periods:

- Approx. 60 subjects with established diagnosis of heart failure with preserved ejection fraction (HFpEF; EF ≥ 45%) (Cohort 1) and
- Approx. 20 subjects with established diagnosis of heart failure with reduced ejection fraction (HFrEF; EF ≤ 35%) (Cohort 2).

All patients will receive the AVIVO / VitalPatch biosensor at 5 monitoring periods (5 patches each subject in total, monitoring period 7 / 5 days each period) and the DynaPort Move Monitor (belt) at 2 monitoring periods (7 day monitoring each period). Results from both devices are not visible to investigator and subjects to avoid bias on treatment decisions.

Biomarkers will be investigated during the hospital stay (only in case patient is hospitalized), at visit 1, and at visit 4. A 6-minute walking test will be performed at visit 1 / discharge and after 11-12 weeks.

Design overview

Abbreviations: KCCQ = Kansas City Cardiomyopathy Questionnaire score; QS = Questionnaire for patient reported outcomes (daily and weekly); 6MWD = 6 minute walking distance; FUP = follow up visit

4. General Statistical Considerations

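### The SAP never separates patients entering at discharge from ambulatory patients, so its mean changes depend on an unreported entry-route mix

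*SAP*

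**What the plan says.** SAP section 3 keeps both entry routes: "Patients hospitalized due to heart failure as well as ambulatory patients with heart failure will be included in this study". Protocol 6.1, criterion 4, defines them as alternatives. One is "Worsening heart failure requiring hospitalization for the initiation of intensification of heart failure therapy". The other is "Ambulatory patients with a history of heart failure on individually optimized treatment with HF medications", with that treatment in place for at least 12 weeks. In Protocol Table 9-1, Day 0 is discharge for the first group and an ambulatory visit for the second.

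The Amendment 3 rationale (Protocol 15.3.1, Modification 1) says that stable ambulatory patients were added "to also gain further insights into this group, in comparison to the hospitalized patients with worsening heart failure". Protocol section 5 says that baseline values and SDs of activity measures are to be estimated "to give information for sample size calculations in subsequent trials".

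In SAP section 3 a cohort is an ejection-fraction class. Cohort 1 is "Approx. 60 subjects with established diagnosis of heart failure with preserved ejection fraction", and Cohort 2 is about 20 with reduced ejection fraction. For the belt, SAP 6.5.4.1 says that "The DynaPort parameters mentioned above will be summarized by cohort/total and visit using descriptive statistics". Its mixed model has visit, baseline value and a random subject effect. Its only subgroups are worsening versus no worsening on 6MWD, KCCQ and PRO.

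**The concern.** The two routes enter at different points in the disease course. The first belt week (Days 9-16) begins about nine days after discharge for one group; for the other, Day 9 has no such anchor. 6MWD, KCCQ and biomarkers are measured at Visit 1 itself, which for the first group is discharge. If discharged patients are still recovering and ambulatory patients are near a plateau, a pooled change is a weighted average of two different courses, with weights set by recruitment.

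A later trial that enrols only one kind of patient would then plan from a mean change that describes neither. The baseline covariate in the mixed model does not repair this, because it adjusts for where a patient starts and not for a different course afterwards. A smaller symptom of the same gap is that the impression-of-change items in Protocol Appendix 16.1 ask about change since hospital discharge, while SAP 6.5.2.2 tabulates them for everyone.

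**Working it through.** **Plan's own figure.** The target is 60 + 20 = 80 completers. Protocol 10.4 states that no power modelling was done, and neither document gives an SD, an effect size, the achieved number or the split by entry route. The target cannot be derived further, and everything numerical below rests on stated assumptions.

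**Step 1: search the SAP for entry route.**

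| SAP section | Grouping or model terms | Entry route used? |
|---|---|---|
| 6.5.1 6MWD | visit, cohort/total, worsening class | no |
| 6.5.2.1 KCCQ | cohort, total, worsening class | no |
| 6.5.2.2 PRO | frequency counts, worsening class; model: visit, baseline, subject | no |
| 6.5.3 Biomarkers | cohort/total, visit | no |
| 6.5.4.1 DynaPort | cohort/total, visit; same model; worsening subgroups | no |

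SAP 7.2 and the footnotes on unaddressed objectives in SAP section 2 do not mention entry route. The descriptive tables therefore pool route within each ejection-fraction cohort, and the two mixed models pool both route and ejection-fraction class.

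**Step 2: effect on the mean.** Let w be the share entering at discharge and D their mean change in within-group SDs of change. Assume the ambulatory mean change is 0. The pooled mean change is w × D.

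| D | w = 0.25 | w = 0.50 | w = 0.75 |
|---|---|---|---|
| 0.3 | 0.075 | 0.15 | 0.225 |
| 0.5 | 0.125 | 0.25 | 0.375 |
| 0.8 | 0.20 | 0.40 | 0.60 |

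At D = 0.5 and w = 0.50 the report would show 0.25 SD: half the change in one group, and a change the other group does not have. For fixed D, the result varies threefold over this range of w.

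**Step 3: effect on the SD.** The pooled SD of change is the within-group SD times √(1 + w(1−w)D²).

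- w = 0.50: D = 0.3 gives √1.0225 = 1.011; D = 0.5 gives √1.0625 = 1.031; D = 0.8 gives √1.16 = 1.077.
- w = 0.25 or 0.75: 1.008, 1.023 and 1.058.
- 10% ambulatory (w = 0.90): D = 0.5 gives √(1 + 0.09 × 0.25) = 1.011.

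The inflation is thus about 1-8% for w from 0.25 to 0.75, and about 1% at D = 0.5 if only one patient in ten was ambulatory.

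**Step 4: precision after a split.** The 90% half-width for the difference in mean change is 1.645 × √(1/n₁ + 1/n₂), in SDs.

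| Total N | 50:50 | 25:75 |
|---|---|---|
| 80 | 0.37 | 0.42 |
| 40 | 0.52 | 0.60 |
| 20 | 0.74 | 0.85 |

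**Step 5: what a model can carry.** There are two belt periods (Days 9-16 and 77-84). SAP 4.5.1 puts baseline at the first visit after screening, but Table 9-1 has no belt at Visit 1, so I take the first belt period as the belt baseline. One response per patient then remains, and a route-by-visit term collapses into a route main effect. If the first period were also kept as a response, it would be regressed on itself. The PRO diary follows the same two periods.

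**Step 6: calendar time.** Amendment 3 is dated 21 Feb 2020, and the SAP dates the pandemic from 11 Mar 2020. The gap is 8 + 11 = 19 days (2020 was a leap year).

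**The case against.** The strongest reply is that nothing promised has been dropped. No objective in Protocol section 4 or SAP section 2 compares the two routes. Protocol 10.1 singles out ejection fraction as the stratification factor, and 10.3.3.1 allows further covariates only as an unnamed option. The Amendment 3 rationale also speaks of covering the whole clinical spectrum, which a mixed sample serves. This stands: a reader might infer that a planned analysis was abandoned, but the comparison appears only as the reason for admitting ambulatory patients. It is still the stated reason, and it gets no output.

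Second, the ambulatory share is unknown and may be small, because ambulatory entry opened late and recruiting stopped early. That stands too, and is a reason to report the share.

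Third, recovery against steady state is partly an assumption. The belt goes on at Day 9 and misses the earliest recovery. The Amendment 3 overview mentions patients seen at unplanned outpatient visits, and criterion 4 accepts a heart-failure hospitalisation in the past 12 months. Separate display would show whether the courses differ.

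Fourth, cells will be small, especially in HFrEF. This limits precision and modelling, but it does not prevent counts, plots and listings by route.

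The individual-data plots and worsening subgroups already planned show some heterogeneity, but without a route label they cannot attribute it.

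**Conclusion.** The omission is certain for the SAP analyses in 6.5.1 to 6.5.4.1. It does not extend to AVIVO and VitalPatch data, which SAP 4.1 leaves to biomarker analyses that these documents do not describe.

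The consequence is conditional. The main harm is a mean change that moves with the entry-route mix, by the factor w if ambulatory patients are flat. Neither w nor the size of post-discharge change is given.

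A reader might go further and infer that later sample sizes would be badly wrong. At a 50:50 mix the variance factor is 1 + 0.25 × 1.0² = 1.25 for a 1.0 SD difference and 1 + 0.25 × 1.5² = 1.56 for 1.5 SD. Nothing in the documents supports differences that large, and the error arises only if the later trial enrols a single route; for a similarly mixed trial the pooled SD is the relevant one.

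This is worth correcting as a matter of description. It does not invalidate the study.

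**What to change.** - Derive entry route and report the number of patients per route by ejection-fraction cohort. Route should follow from which arm of criterion 4 was met, from whether Visit 1 was a discharge or an ambulatory visit, and from the screening biomarker sample, which Table 9-1 limits to hospitalised patients. No dedicated data field is described, so the derivation should be checked.
- In SAP 6.5.1 to 6.5.4.1, present level, change and SD by entry route, overall and within ejection-fraction cohort where numbers allow. Mark individual plots and listings by route.
- If a model is used, fit the second-period value adjusted for the first (or the change) with entry route as a main effect. Do not add route-by-visit to the planned baseline-adjusted model, where it cannot be estimated.
- Tabulate by route the PRO items that refer to hospital discharge.
- State that the contrast is descriptive and tied to calendar time and the pandemic.

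The cost is SAP wording, extra table columns and the derivation; provided route can be derived as above, no new data collection is needed. The downside is small cells and wide intervals. If cells are too sparse to tabulate, route-marked plots and listings with a stated limitation are enough.

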Plan for statistical analysis	
Statistical analyses will be of explorative and descriptive nature. The study is not aimed to confirm or reject pre-defined hypotheses.
 
All variables will be analyzed descriptively with appropriate statistical methods: categorical variables by frequency tables (absolute and relative frequencies) and continuous variables by sample statistics (i.e. mean, standard deviation, minimum, median, quartiles and maximum). Continuous variables will be described by absolute value and as change from baseline per analysis time point, if applicable.
 
The variability of biomarkers assumed to be normal distributed will be analyzed using a linear mixed effect model with subject as random factor, and time as fixed factor, possibly including additional covariates as may result from the assessment at baseline for subject stratification or as required for clinical interpretation. Based on this model, point estimates (LS-Means) and exploratory 90% confidence intervals will be calculated for comparing baseline and 3 months data. For biomarkers assumed to be log-normal distributed, the logarithms of the biomarker concentration will be analyzed, and results will be reported as ratio for comparing baseline and 3 months data.
 
All analyses will be performed for the total study population (overall analysis). Subjects wearing at least once the VitalPatch biosensor system and for which data was successfully collected over 5 days will be included in the analysis.
 
Sample size and disposition information by analysis time point will be displayed in a frequency table.

 Replacement of AVIVO MPM with VitalPatch Biosensor as per Amendment 2 (Section 15.2)

 Replacement of AVIVO MPM with VitalPatch Biosensor as per Amendment 2 (Section 15.2)

 Adapted to reflect the extension on non-hospitalized subjects as per Amendment 3 (Section 15.3)

 Adapted to reflect the limitations of the VitalPatch biosensor system as per Amendment 3 (Section 15.3)

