### 10.3.3 Analysis of primary and secondary outcomes

#### 10.3.3.1 Assessment of variability

The variability between subjects and within subjects across time for each of the parameters of interest will be described using a linear mixed model (LMM) with subject as random factor, and time as fixed factor, possibly including additional covariates as may result from the assessment at baseline for patient stratification or as required for clinical interpretation.

In addition to effects and interactions of fixed effects parameters LMMs will be used to estimate simultaneously parameters of the variance and covariance components of random effects due to subjects.

The LMM for the parameter of interest (Y) as selected among the molecular and digital biomarkers available (i.e. laboratory parameters and device generated digital data) will have the following base annotation:

$$Y_{st} = \beta_0 + \beta_1 \cdot TIME_t + S_{0s} + \varepsilon_{st}$$

Where S is subject (random) and TIME represents visit, with baseline as reference.

The HF type (preserved/reduced) will be included in the model (here denoted as C), as random factor, and the effect on intercept or slope will be assessed:

$$Y_{st} = \beta_0 + (\beta_1 + C_{1s}) \cdot TIME_t + S_{0s} + C_{0s} + \varepsilon_{st}$$

Where  $C_{1s}$  will be the effect of HF type on the slope (e.g., if changes in physical activity are different between the two sub-populations) and  $C_{0s}$  will be the effect on the intercept (e.g., if the two sub-populations have different baseline values).

Given the high number of parameters involved and the exploratory nature of the study, all of the possible models will not be addressed here, and the base model will be extended as appropriate depending on the specific question to address and the given subset of parameters involved.

Testing of random effects and visualization of residuals will be performed in order to highlight single subjects (or sub-group) showing outstanding or peculiar characteristics.

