Estimates from the model will be used to quantify the ability of a parameter to measure clinically relevant changes over time. The intraclass correlation coefficient (ICC) will be used as key statistic when considering the relative proportion of within- and between-individual variation is the expected correlation among measurements from the same individual, it can indicate the degree of difference between individuals and will also be used as measure reliability (ability to reflect true between-individual differences). For any sample, the ICC will be calculated with estimates from LMMs of both between-individual variance and within-individual variance, according the following:

$$ICC = \tau^2 / (\tau^2 + \sigma^2)$$

---

 Replacement of AVIVO MPM with VitalPatch Biosensor as per Amendment 2 (Section 15.2)

where  $\tau^2$  is a commonly used symbol for between-individual variance (variance of  $S_{0s}$  term in in the base model above) and  $\sigma^2$  for within-individual variance (variance of  $\varepsilon_{st}$  in the base model). Then, ICC will be the proportion of total variance ( $\tau^2 + \sigma^2$ ) attributable to between-individual differences ( $\tau^2$ ).

In addition, point estimates (LS-Means) and exploratory 90% confidence intervals will be calculated for comparing baseline and 3 months data by HF type (preserved/reduced), and may include intermediate time points if available.

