6.5.2 Quality of life / PRO

6.5.2.1 KCCQ

The summary scores “Total Symptom Score”, “Clinical Summary Score”, and “Overall Summary Score” as well as the “Physical Limitation Scores” will be summarized using frequency counts by cohort and total.

A frequency table will be created for the comparison of the subjects with and without observed worsening according to the following definitions:

- Worsening: decrease in KCCQ score by at least 5 points
- No worsening: decrease in KCCQ score by up to 5 points, no change or increased KCCQ score

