6.5.2.2 PRO

The “Overall Activity Score” will be calculated as the sum of the following mean items: walking general, housework, and exercise.

The parameters

- Overall Activity Score
 - o General physical activity item (1 unit change on weekly average score)
 - o Physical activity impression of change item (2 unit change)
 - o Fatigue impression of change item (2 unit change)
 - o Shortness of breath impression of change item (2 unit change)
 - o Swelling impression of change item (2 unit change)

will be summarized using frequency count.

In addition, response with respect to the anchor measures derived from the following individual items

- General physical activity item (1 unit change)

- Physical activity impression of change item (2 unit change)
- Fatigue impression of change item (2 unit change)
- Shortness of breath impression of change item (2 unit change)
- Swelling impression of change item (2 unit change)

will be tabulated using frequency tables.

A frequency table will be created for the comparison of the subjects with and without observed worsening according to the following definitions:

- Worsening: decrease in “Overall Activity Score” by at least 2 units
- No worsening: decrease in “Overall Activity Score” by up to 2 points, no change or increased “Overall Activity Score”

The univariate linear mixed model (LMM) for the repeated values of the “Overall Activity Score” is

$$Y_{ij} = \mu + S_i + v_j + \beta base_i + E_{ij}$$

where μ is a constant common to all observations, S_i is the normally distributed random variable with mean zero and variance σ_d^2 corresponding to subject i , v_j is the fixed effect corresponding to visit j , and E_{ij} is a normally distributed random variable with mean zero and variance σ_e^2 , independent of S_i . The variable “base” is the baseline measurement included as covariate and β is the corresponding regression parameter.

Based on the described LMM, point estimates and 90% confidence intervals for the “Overall Activity Score” will be calculated.

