7.2 Changes in the planned statistical analysis

The planned analysis described in the CSP were revised comprehensively for the following reasons:

- Lower number of subjects included
- Changes in procedure schedule
- Changes of device
- Changes of parameters provided by the vendor

8. References

[1] Integrated Clinical Study Protocol No. BAY 1067197 / 19167, version 4.0, dated 21 FEB 2020

[2] Clinical Pharmacology Standards (CLIPS), version 3.0, dated 05 AUG 2020

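### The SAP's DynaPort mixed model has no HF-type term, so the protocol's type-specific 90% intervals for change are not planned, and SAP 7.2 does not say so

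*SAP*

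**What the plan says.** **Protocol.** Section 10.3.3.1 defines a mixed model for laboratory and device parameters. It extends the model by HF type on the intercept and on the slope; the slope term is there to show "if changes in physical activity are different between the two sub-populations". It then states: "point estimates (LS-Means) and exploratory 90% confidence intervals will be calculated for comparing baseline and 3 months data by HF type (preserved/reduced". The Synopsis plan for statistical analysis is less specific. It says "point estimates (LS-Means) and exploratory 90% confidence intervals will be calculated for comparing baseline and 3 months data" and does not mention HF type.

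**SAP.** The DynaPort model in 6.5.4.1 contains a constant, a random subject effect, a fixed visit effect, a baseline covariate and a residual. Its output is described in one sentence: "Based on the described LMM, point estimates and 90% confidence intervals for the DynaPort parameters will be calculated". HF type appears in the descriptive part: "The DynaPort parameters mentioned above will be summarized by cohort/total and visit using descriptive statistics", with statistics also for the difference to baseline. The only subgroup analyses in that section are by worsening category of 6MWD, KCCQ and PRO.

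**Changes.** SAP 7.2 opens with "The planned analysis described in the CSP were revised comprehensively for the following reasons" and lists four reasons: fewer subjects, the procedure schedule, the device, and the parameters supplied by the vendor. SAP section 2 marks three objectives as not addressed or not meaningfully assessable; none of them concerns HF type.

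**The concern.** The study looks for endpoints for future HFpEF trials (Protocol Synopsis), treats ejection fraction as the stratification factor (Protocol 10.1), and includes HFrEF patients as a plausibility check on the device readouts (Protocol 6.3). With no cohort term, every modelled DynaPort interval describes whatever HFpEF/HFrEF mix was enrolled. The type-specific interval that a planner of an HFpEF trial would want is not produced. Nor is the contrast that would show whether activity changes differently in the two types. A reader who compares the SAP with protocol 10.3.3.1 cannot learn from SAP 7.2 that these outputs were removed, or why.

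The same model has a second gap that must be closed before a cohort term can be added usefully: its baseline covariate is undefined for DynaPort.

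**Working it through.** **1. The two models.**

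| Element | Protocol 10.3.3.1 | SAP 6.5.4.1 |
|---|---|---|
| Subject | random | random |
| Time | fixed, baseline as reference | fixed visit |
| HF type, level | included | absent |
| HF type, change | included | absent |
| Baseline covariate | not in the base model | included |
| 90% interval by HF type | planned | not stated |

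The SAP does not forbid fitting the model within each cohort, but it does not plan it.

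**2. The baseline covariate.** SAP 4.5.1 sets baseline at the first visit after screening, which is Visit 1 (Day 0). Protocol Table 9-1 has the belt worn twice: from Visit 2 (Day 9) and from Visit 3 (Day 77). No DynaPort value exists at Visit 1, so the covariate has no value. If wearing period 1 is used as the covariate instead, one later period remains per subject. With one response per subject, the data identify only the sum of the subject and residual variances, so the two components in the SAP model cannot be separated. The by-cohort difference to baseline needs the same clarification.

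**3. What pooling does to the estimate.** At 60:20 with complete pairs and no covariate, the pooled change weights the types 0.75 and 0.25. With assumed changes of +0.2 and -0.6, the pooled change is 0.75 × 0.2 + 0.25 × (-0.6) = 0. This only shows that a pooled change can hide opposite changes. The by-cohort descriptive means would still show them.

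**4. Precision of the missing outputs.** The plan has no figure to reproduce: Protocol 10.4 says no power modelling was done, and the target is 60 + 20 = 80. The half-widths below are in SDs of change and assume complete pairs and a common SD, with N = n1 + n2:

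- one type: t(0.95, N-2)/√n
- contrast: t(0.95, N-2) × √(1/n1 + 1/n2)
- pooled: t(0.95, N-1)/√N

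At 60:20, t(0.95, 78) = 1.665. HFpEF is 1.665/√60 = 0.215, HFrEF is 1.665/√20 = 0.372, the contrast is 1.665 × √(1/60 + 1/20) = 0.430, and pooled is 1.664/√80 = 0.186.

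| HFpEF:HFrEF | HFpEF | HFrEF | Contrast | Pooled |
|---|---|---|---|---|
| 60:20 (target) | 0.215 | 0.372 | 0.430 | 0.186 |
| 30:10 (assumed) | 0.308 | 0.533 | 0.616 | 0.266 |
| 15:5 (assumed) | 0.448 | 0.775 | 0.895 | 0.387 |

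**5. If period 2 is regressed on period 1 plus cohort.** With equal variances in both periods and within-subject correlation r, the residual SD is √((1+r)/2) SDs of change. The 60:20 contrast half-width becomes about 0.37, 0.40 or 0.42 at assumed r of 0.5, 0.7 or 0.9, against 0.43.

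**The case against.** The study is exploratory, and Protocol 10.1 leaves statistical details to the SAP. The Synopsis and 10.1 both call for an overall analysis, and the Synopsis gives the 90% intervals without HF type, so the SAP agrees with one of the two protocol statements. No listed objective is a between-type comparison; 10.3.3.1 offers it as an example. The SAP does disclose, in general terms, that numbers fell and the analysis was reworked. It itemises no dropped method, and the intraclass correlation and canonical correlation of the protocol are also absent from it. With 5 HFrEF patients an interval of plus or minus 0.78 SD says little.

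Most of this stands, and it limits the weight of the point. It does not remove it. Section 10.3.3.1 is the detailed statement, it names HF type explicitly, and device data are within its scope. Low numbers are a plausible reason, but the SAP does not link them to this change, and it keeps worsening subgroups that divide the same small sample. The plausibility-check role of HFrEF weakens the case for the contrast but strengthens the case for a separate HFpEF interval.

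A reader might also infer that the PRO model in SAP 6.5.2.2 breaks the same protocol commitment. It does not: 10.3.3.1 limits the modelled parameters to laboratory and device data, so the PRO model is an addition by the SAP.

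**Conclusion.** The point holds for DynaPort. The type-specific 90% intervals and the between-type difference in change, both provided for in protocol 10.3.3.1, have no counterpart in SAP 6.5.4.1. The change is not named in SAP 7.2, and the model's baseline covariate has no value as defined. Severity is low to moderate.

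Three stronger readings are not supported:

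- **By-type information on change is lost.** By-cohort means, SDs and differences to baseline stay in the plan. Once the baseline is clear, a reader could build an interval from n, mean and SD of the change in complete pairs. What is missing is a planned interval and contrast.
- **The pooled interval will be presented as type-specific.** The SAP does not say this.
- **The revision was undisclosed.** It was disclosed in general terms, without this item.

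The half-widths rest on a common SD of change and complete pairs. The 30:10 and 15:5 splits are assumptions, because the documents give no realised numbers by type.

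A minor related point is not a departure from the protocol. The PRO Overall Activity Score uses the same model form, and its diary runs alongside the belt, so it has the same baseline problem. Its summary, "will be summarized using frequency count", names no cohort, while the neighbouring KCCQ section says "will be summarized using frequency counts by cohort and total".

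**What to change.** In SAP 6.5.4.1:

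1. State wearing period 1 as the DynaPort baseline, for the model and for the descriptive difference to baseline.
2. Use one of two models. (a) Take both periods as responses, with fixed cohort, period and cohort-by-period, random subject and no baseline covariate. (b) Model period 2, or the change, on period 1 plus cohort. Model (a) estimates the difference in mean change, which is what the protocol's slope term describes. Model (b) compares the types at equal period 1 activity; in non-randomised cohorts that can be a different quantity, so the SAP should say which is meant. Enter cohort as fixed: two levels are too few to estimate a random-effect variance, which the protocol's notation would require.
3. Report by-cohort change and the cohort difference with exploratory 90% intervals beside the pooled estimate.
4. If HFrEF numbers are too small, keep the by-cohort descriptives and record in SAP 7.2 that the by-type modelled estimates of protocol 10.3.3.1 were dropped, and why.

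In SAP 6.5.2.2, state the PRO baseline and add a by-cohort summary of the Overall Activity Score for consistency.

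The cost is SAP wording and a few table rows from data already collected. The drawback is wide HFrEF intervals, so the number of patients behind each should be shown with it.
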